#### **4.2.4 Previous and Concomitant Medications and Procedures**

Prior and concomitant medications and procedures will be listed for all patients in the SAF.

Concomitant medications will be summarized by chemical subgroup (ATC 4th level), and preferred WHO name for the SAF. Patients with the same concomitant medication/procedure multiple times will be counted once per medication/procedure. A medication/procedure that can be classified into more than one chemical and/or therapeutic subgroups will be presented in each subgroup.

#### **4.2.5 Study drug administration**

Individual patient data for study drug administration will be listed for all patients in the SAF.

### **4.3 Analysis of Primary Safety Endpoint**

The primary endpoint of this study is the incidence of Grade 3 and Grade 4 TRAEs (see Section [3.2.3.1](#)) which occur within the first six months (ie, up to and including the 183rd day) after the initiation of durvalumab. Any Grade 3 or Grade 4 TRAEs which started after the 183rd day of the study, or after the 90th day following discontinuation of durvalumab, or after the start of

subsequent anti-cancer therapy will not be included.

The number and percentage (and exact Clopper-Pearson 95% CI) of patients with NCI CTCAE Grade 3 or Grade 4 TRAEs, both overall and for those occurring within the first six months after initiation, will be summarized for the SAF for all patients and within the WHO/ECOG PS 0/1 and PS 2 groups. This summary will also be graphically presented as a bar chart. The number and percentages of patients with NCI CTCAE Grade 3 or Grade 4 TRAEs will also be summarized by SOC and PT.

## **4.4 Analysis of Secondary Efficacy Endpoints**

### **4.4.1 Progression-Free Survival**

Kaplan-Meier plots and descriptive statistics will be provided for PFS. Summary statistics will include lower and upper quartile and median PFS, PFS12 (Day 365) and PFS24 (Day 730).

Summaries of the number (%) of patients experiencing a PFS event (overall and also at Month 12 and Month 24) and the type of event (disease progression or death) will be provided.

All summary statistics will be presented with the appropriate 95% CI.

If necessary, a sensitivity analysis will be conducted to assess the potential impact of COVID-19 related deaths on PFS. That is, patients who had a PFS event due to death where the primary or secondary cause of death was COVID-19 infection or COVID-19 infection was reported as a fatal AE, will be censored at the last evaluable RECIST 1.1 assessment prior to COVID-19 infection related death.

### **4.4.2 Overall Survival**

The following numbers (%) of patients in the SAF will be presented at 12month (Day 365) intervals and overall: those who have died, those still in survival follow-up, those lost to follow-up, those who withdrew consent, and those with censored OS.

Kaplan-Meier plots and descriptive statistics will be presented for OS. Summaries will include the lower and upper quartile and median OS, and estimates of OS12 (Day 365), OS24 (Day 730) and OS36 (Day 1095).

All summary statistics will be presented with the appropriate 95% CI.

If necessary, a sensitivity analysis will be conducted to assess the potential impact of COVID-19 related deaths on OS. That is, patients who had a death event where the primary or secondary cause of death was COVID-19 infection or COVID-19 infection was reported as a fatal AE, will be censored at the date of their COVID-19 infection related death.

### **4.4.3 Objective Response Rate**

The ORR will be estimated for the SAF and will be presented with the corresponding exact 95% CIs.

The number (%) of patients with a confirmed response and the number (%) of patients with a single visit response (ie, an unconfirmed response) will also be presented.

Best objective response (BoR) will be summarised by n (%) for each category (CR, PR, SD, PD and NE).

#### **4.4.4 Duration of Response**

A Kaplan-Meier plot and descriptive statistics will be provided for the DoR and the respective Time to onset of first response for patients in the SAF who had responded to treatment (see Section 3.3.5). Summary statistics will include: lower and upper quartile and median DoR with appropriate 95% CIs.

#### **4.4.5 Time to Lung Cancer Mortality (NSCLC-Related Death)**

The following numbers (%) of patients in the SAF will be presented at Month 12 (Day 365) intervals and overall: those with an NSCLC-related death, those still in survival follow-up, those lost to follow-up, those who withdrew consent, and those with censored time to lung-cancer mortality (separately for those who died from a cause not related to NSCLC and other reasons for censoring, as well as overall).

Kaplan-Meier plots and descriptive statistics will be presented for time to NSCLC-related mortality. Summaries will include the lower and upper quartile and median lung cancer mortality and estimates at Month 12 (Day 365), Month 24 (Day 730), and Month 36 (Day 1095).

All summary statistics will be presented with the appropriate 95% CI.

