- $PFS \text{ (days)} = \text{Date of event or Censor date} - \text{treatment start date} + 1$
- Patients who have not progressed or died at the time of analysis will be censored at the time of the latest date of assessment from their last evaluable assessment. However, if the patient progresses or dies after 2 or more missed visits, the patient will be censored at the time of the latest evaluable assessment prior to the 2 missed visits. If the patient has no evaluable visits or does not have baseline data, he/she will be censored at Day 1 unless he/she dies within 2 visits of baseline, in which case the date of death is the event date.
- 8 **OS:** Defined as the time from the first date of treatment until death due to any cause.
- $OS \text{ (days)} = \text{Death date or Censor date} - \text{treatment start date} + 1$
- Any patient not known to have died at the time of analysis will be censored based on the last recorded date on which the patient was known to be alive.
- 9 **Lung cancer mortality (NSCLC-related death):** Defined as the time from the date of treatment start until death due to lung cancer.
- $\text{Time to NSCLC-related deaths (days)} = \text{NSCLC-related death date or Censor date} - \text{treatment start date} + 1$
- Any patient not known to have died due to lung cancer will be censored based on the last recorded date on which the patient was known to be alive or died due to reason other than lung cancer.
- 10 **ORR:** Based on Investigator-assessed response to treatment of CR and PR, per RECIST1.1.
- 11 **DoR:** Defined as the time from the date of first documented response per RECIST1.1 until the first date of documented progression per RECIST1.1 or death in the absence of disease progression

DoR (days) = Date of PFS event or censoring – Date of first response +1

The end of response should coincide with the date of progression or death from any cause used for the PFS endpoint. If a patient does not progress following a response, then the patients' DoR will be censored at the PFS censoring time. DoR will not be defined for those patients who do not have a documented response.

12

CCI [REDACTED]

13 **Treatment duration:** Defined as Treatment end date – Treatment start date +1; will be summarized.

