9.5.2.2 Efficacy variables

Efficacy data will be reported for patients overall and separately for the cohorts of WHO/ECOG PS 0 to 1 and 2 patients whenever possible.

Progression-free survival

The median PFS together with the corresponding 95% CIs will be reported using Kaplan-Meier product limit methods. In addition, the proportion of patients who are progression-free at 12 and 24 months will be presented.

Overall survival

The median OS together with the corresponding 95% CIs will be reported using the Kaplan-Meier product limit methods. In addition, the proportion of patients who are alive at 12, 24, and 36 months will be reported.

Lung cancer mortality (NSCLC-related deaths)

The median time to NSCLC-related death together with the corresponding 95% CIs will be reported using the Kaplan-Meier product limit methods.

Objective response rate

The ORR, based on Investigator assessments (following RECIST 1.1 criteria; see [Appendix F](#)), together with the corresponding 95% CIs will be reported.

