#### 1.1.2 Secondary Objectives

Secondary Efficacy Objectives	Endpoints / Variables
To assess the efficacy of durvalumab treatment in terms of progression-free survival (PFS) and overall survival (OS)	Median PFS according to Response Evaluation Criteria in Solid Tumours version 1.1 (RECIST 1.1) as assessed by the Investigator  PFS12 and PFS24 according to RECIST 1.1 as assessed by the Investigator  Median OS, OS12, OS24, and OS36
To further assess the efficacy of durvalumab treatment in terms of objective response rate (ORR) and duration of response (DoR)	ORR according to RECIST 1.1 as assessed by the Investigator  DoR according to RECIST 1.1 as assessed by the Investigator
To assess the efficacy of durvalumab treatment in terms of lung cancer mortality	Lung cancer mortality

Secondary Safety Objectives	Endpoints / Variables
To further assess the safety and tolerability profile of durvalumab treatment, including all adverse events (AEs)	AEs, serious adverse events (SAEs), adverse events of special interest (AESIs), immune-mediated adverse events (imAEs), physical examinations, vital signs including blood pressure (BP) and pulse rate, respiratory rate, temperature, ECGs, and laboratory findings including clinical chemistry, haematology and urinalysis

Note: Analysis of ORR and DoR will be based upon Investigator assessment according to RECIST 1.1. Prior irradiated lesions may be considered measurable and selected as target lesions providing they fulfil the other criteria for measurability.

Note: An AESI is an AE of scientific and medical interest specific to understanding of the durvalumab. AESIs for durvalumab include, but are not limited to, events with a potential inflammatory or immune-mediated mechanism and which may require more frequent monitoring and/or interventions such as steroids, immunosuppressants and/or hormone replacement therapy.

Note: An imAE is defined as an AESI that is associated with drug exposure and is consistent with an immune-mediated mechanism of action and where there is no clear alternate etiology.

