### 3.3.6 Lung Cancer Mortality

The lung cancer mortality (NSCLC-related death) is assessed using the deaths which are reported as 'NSCLC-related' and is defined as the time (days) from the date of first dose of durvalumab until date of death due to lung cancer as follows:

- $\text{Time to lung cancer mortality} = (\text{date of NSCLC-related death or censoring}) - (\text{date of first dose of durvalumab}) + 1$

Any patient not known to have died at the date of DCO will be censored at the last recorded date at which the patient was known to have been alive, or at date of DCO, if known afterwards.

The date that an individual patient was last known to be alive will be identified exclusively using the data recorded within the SURVIVE and DEATH modules of the electronic case report form (eCRF).

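### Lung cancer mortality is estimated by Kaplan-Meier with deaths from other causes censored, so it overstates the proportion of patients who die of lung cancer

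*SAP*

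**What the plan says.** SAP 1.1.2 lists the objective "To assess the efficacy of durvalumab treatment in terms of lung cancer mortality" among the secondary efficacy objectives, and the protocol does the same. Under SAP 3.3.6 the event is a death reported as NSCLC-related, timed from the first dose.

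Censoring: under Protocol 9.4, item 9, a patient not known to have died of lung cancer is "censored based on the last recorded date on which the patient was known to be alive or died due to reason other than lung cancer". SAP 4.4.5 follows this by tabulating the censored patients "separately for those who died from a cause not related to NSCLC and other reasons for censoring, as well as overall". The censoring rule in SAP 3.3.6 covers only patients not known to have died by the data cut-off, so it does not say what happens to someone who died of another cause.

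Estimation: Protocol 9.5.2.2 states: "The median time to NSCLC-related death together with the corresponding 95% CIs will be reported using the Kaplan-Meier product limit methods". SAP 4.4.5 adds: "Kaplan-Meier plots and descriptive statistics will be presented for time to NSCLC-related mortality", with quartiles, the median and estimates at Days 365, 730 and 1095, each with a 95% CI. Efficacy results are given overall and by performance status (PS) cohort (Protocol 9.5.2.2, SAP 4.1.1).

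Neither document mentions competing risks, a cumulative incidence function, or the independence assumption that this censoring requires.

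**The concern.** Censoring says that the patient is still at risk and that the event may yet happen unseen. That is false for someone who has died of another cause. Kaplan-Meier nevertheless spreads that patient's weight over those still at risk, as if a lung cancer death would have followed at their rate. The result describes a hypothetical population in which nobody dies of anything else, and only if the two causes of death are independent, which the data cannot verify.

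A clinical reader will take a 36-month lung cancer mortality figure as the share of treated patients who have died of lung cancer, and the median as the time by which half have. The planned estimates are neither. The plan itself expects other deaths: SAP 4.4.1 and 4.4.2 provide for sensitivity analyses of COVID-19 deaths for PFS and OS, but there is none for this endpoint.

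**Working it through.** **No planned figure to reproduce.** Neither document gives an expected lung cancer mortality or a share of deaths due to other causes.

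**Direction.** At each NSCLC death, with Y patients at risk, 1 − KM rises by S₁/Y and the Aalen-Johansen cumulative incidence rises by S/Y. S₁ is Kaplan-Meier survival counting only NSCLC deaths; S is all-cause survival. Since S ≤ S₁, 1 − KM can never be the smaller. The two agree only if no non-NSCLC death precedes an NSCLC death. This needs no distributional assumption.

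**Size: inputs.**
- Median all-cause survival 23.2 months. Protocol 2.2.1 reports this for the observation arm of a phase III consolidation-docetaxel study. It is background, not a planning assumption for this trial.
- Share of deaths that are non-NSCLC: assumed, 5% to 30%. Write s for the NSCLC share.
- Constant cause-specific hazards: assumed.

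**Formulas.** L = ln 2 / 23.2 = 0.02988 per month.
- 1 − KM(t) = 1 − exp(−sLt)
- Cumulative incidence CIF(t) = s[1 − exp(−Lt)]
- KM median = 23.2/s
- Time for the CIF to reach 50% = −ln(1 − 0.5/s)/L

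**Worked case, 20% non-NSCLC (s = 0.8), 36 months.** Lt = 1.0756. 1 − KM = 1 − exp(−0.8605) = 57.7%. All-cause mortality = 1 − exp(−1.0756) = 65.9%, so CIF = 0.8 × 65.9% = 52.7%. KM median = 23.2/0.8 = 29.0 months; CIF time to 50% = 0.9808/0.02988 = 32.8 months.

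**Results** (1 − KM vs CIF; excess taken before rounding):

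| Non-NSCLC share | 12 months | 24 months | 36 months | Excess at 36 months | Time to 50%, KM vs CIF (months) |
|---|---|---|---|---|---|
| 5% | 28.9 vs 28.6% | 49.4 vs 48.6% | 64.0 vs 62.6% | 1.4 points | 24.4 vs 25.0 |
| 10% | 27.6 vs 27.1% | 47.6 vs 46.1% | 62.0 vs 59.3% | 2.7 points | 25.8 vs 27.1 |
| 20% | 24.9 vs 24.1% | 43.7 vs 40.9% | 57.7 vs 52.7% | 5.0 points | 29.0 vs 32.8 |
| 30% | 22.2 vs 21.1% | 39.5 vs 35.8% | 52.9 vs 46.1% | 6.8 points | 33.1 vs 41.9 |

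**Sensitivity to median survival.** The protocol's other background figure, 5-year survival of about 15%, corresponds to a median of 21.9 months. The 36-month excess is then 2.9, 5.4 and 7.4 points at 10%, 20% and 30%. If median survival were 40 months (assumed), it would be 1.2, 2.2 and 2.9 points.

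**Coherence.** In the 20% case, 1 − KM for non-NSCLC death at 36 months is 1 − exp(−0.2151) = 19.4%. The two causes then add to 57.7 + 19.4 = 77.1%, against all-cause mortality of 65.9%. The CIFs add to 65.9% exactly.

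**Simulation.** With n = 120, a 20% share and assumed follow-up of 27 to 45 months, 1,500 simulated trials average 57.5% vs 52.5% at 36 months.

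**The case against.** - **The effect may be small.** This stands. At a 5% share the 36-month excess is 1.4 points. Near 50%, ignoring censoring, the sampling half-width is about 9 points for n = 120 (1.96 × √(0.25/120)) and 18 for n = 30. But the error goes one way, and the reported interval is centred on the wrong quantity.
- **The raw counts are planned anyway.** SAP 4.4.5 tabulates NSCLC and other deaths at 12-month intervals, SAP 4.5.1 splits deaths by cause, and OS is reported. This limits the harm but does not correct the curve, the median or the landmark estimates. Nor is a crude Month-36 percentage a substitute: the final cut-off comes when the last patient could have had 24 months of treatment plus 90 days, so some patients may lack 36 months of follow-up.
- **Kaplan-Meier here is a legitimate cause-specific quantity under independence.** True, and the plan never calls it the proportion dying of lung cancer. But it does not state the assumption either. This argues for labelling the Kaplan-Meier figure, not for leaving it as the only estimate.

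Stronger readings that the documents do not support:
- A reader might infer that the PS 2 figure is distorted more than the PS 0 to 1 figure. No document gives causes of death by cohort, and the cohorts are not formally compared.
- A reader might infer far larger distortions, or a Kaplan-Meier median for a curve that never reaches 50%. Those need 40% or more of deaths to be non-NSCLC, which nothing supports. At 40% the CIF reaches 50% at 60.0 months, beyond a study running from Q2 2019 to Q2 2023, about 48 months. At 50% the Kaplan-Meier median would be 23.2/0.5 = 46.4 months, at the very edge of follow-up.

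**Conclusion.** The concern holds. Censoring non-NSCLC deaths makes the planned estimates at least as large as the cumulative incidence of lung cancer death, and larger once other deaths precede NSCLC deaths. The direction is certain; the size is not. On a median survival of 23.2 months and constant hazards, the 36-month excess is about 3, 5 or 7 points at a 10%, 20% or 30% non-NSCLC share, and the median is about 1, 4 or 9 months early. The last gap depends on a time of 41.9 months, which only early enrolees could inform. Longer survival shrinks the excess at 36 months.

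This is worth correcting but not critical: the endpoint is secondary and descriptive, no hypothesis is tested, and the primary safety result is untouched.

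A reader might also infer that deaths of unknown cause should count as lung cancer deaths in the main analysis. SAP 3.3.6 does not support that, because it counts only deaths reported as NSCLC-related. Nor would it reliably lower the figure. With assumed 36-month survival of 45% and deaths 65% NSCLC, 10% unknown and 25% other, the planned 1 − KM (unknowns censored) is 1 − 0.45^0.65 = 40.5%. The CIF with unknowns counted as NSCLC is 0.75 × 55% = 41.3%.

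**What to change.** - **SAP 3.3.6:** state that non-NSCLC death is a competing event. Keep the event as deaths reported as NSCLC-related.
- **SAP 4.4.5:** make the Aalen-Johansen cumulative incidence of NSCLC-related death the main estimate, with 95% CIs at Days 365, 730 and 1095, overall and by PS cohort.
- **Median:** either keep the protocol's Kaplan-Meier median, labelled as a cause-specific quantity that assumes independent censoring, or replace it with the time at which the cumulative incidence reaches 50%, if it does.
- **Unknown cause:** count these deaths as NSCLC-related in a sensitivity analysis only.
- **SAP Section 6:** record the change, because the Kaplan-Meier median is named in the protocol synopsis and Section 9.5.2.2, and Section 8.1 lists the median among the key efficacy endpoints.

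Cost: one additional standard analysis on data already collected, some SAP wording, and a documented change from the protocol.

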### **4.5 Analysis of Secondary Safety Endpoints**

#### **4.5.1 Adverse Events**

All AEs reported up until 90 days following completion or discontinuation of durvalumab treatment or until the initiation of the first subsequent therapy (whichever occurs first) will be included in the summaries unless explicitly stated otherwise below.

All AEs will be summarised descriptively, in terms of number of patients (n) and percentage of patients (%) reporting the event by MedDRA SOC and PT.

Listings of AEs will include the date of onset, date of resolution (if AE is resolved) and investigator's assessment of severity, relationship to durvalumab, and NCI CTCAE Grade. Separate listings will be produced for all AEs, TRAEs, SAEs, AESIs, imAEs, AEs with outcome of death, AEs leading to discontinuation of durvalumab, AEs leading to discontinuation of study. Listings of AESIs and imAEs will also include the additional information (eg, intervention, dose, duration of therapy etc.) recorded for these AEs. All AEs that are not treatment-emergent will be flagged in the data listings and the time of onset will be flagged as 'pre-treatment', 'post-treatment and no other anti-cancer therapy' and 'after initiation of other anti-cancer therapy'.

An overall summary of AE data will be presented including the number and percentage of patients reporting the following:

- At least one AE

- At least one TRAE
- At least one AE of CTCAE Grade 3 or Grade 4
- At least one TRAE of CTCAE Grade 3 or Grade 4
- At least one SAE
- At least one Serious TRAE
- At least one AE leading to discontinuation of study treatment
- At least one TRAE leading to discontinuation of study treatment
- At least one AE leading to treatment interruption
- At least one TRAE leading to treatment interruption
- At least one AE with outcome of death
- At least one TRAE with outcome of death
- At least one AESI
- At least one TRAE of special interest (AESI)
- At least one imAE (and exact Clopper-Pearson 95% CI)
- At least one immune-mediated TRAEs

The following summaries including the number and percent of patients by SOC and PT will be presented separately:

- All AEs / TRAEs
- All AEs / TRAEs of CTCAE Grade 3 or Grade 4
- All TRAEs of CTCAE Grade 3 or Grade 4 occurring within the six months of first dosed date
- All TRAEs which starts within 90 days after last dose of durvalumab (irrespective of start of subsequent anti-cancer therapy)
- All AEs
  - This summary will include an AE event rate (per 100 patient years) for each PT. The number of patients with an AE in each PT is divided by the sum of the actual exposure to durvalumab (days) (see section 3.2.8) over all patients. This is multiplied by 365.25 x 100 to create an event rate per 100 patient years.
- All AEs by maximum CTCAE Grade
- All AEs / TRAEs with outcome of death
- All SAEs / Serious TRAEs
- All AEs / TRAEs leading to discontinuation from durvalumab (Note: Reason for discontinuation recorded on the patient disposition page)
- All AEs / TRAEs leading to dose interruption/discontinuation of durvalumab (Note: Reason for discontinuation recorded on the patient disposition page)

A summary of most common AEs and another summary of most common AEs with CTCAE Grade 3 or higher, including all events that occur in at least 2.5% of patients overall will be presented by PT, by decreasing frequency. This cut-off may be modified after review of the data. The raw percentage will be compared to the cut-off, without applying any rounding to the percentage value (ie, a TEAE with frequency of 2.4% will not appear in the table if a cut-off is 2.5%).

A summary of deaths will be provided with the following information:

- Number of deaths (NSCLC-related, non-related, and unknown)
  - Number of deaths during the on-treatment study period up until 90-day follow-up and prior to initiation of first subsequent therapy
  - Number of deaths occurring more than 90 days after the last dose of durvalumab or after initiation of first subsequent therapy

Listings of key patient information for Deaths and SAEs will be provided.

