### **3.2.3 Adverse Events**

Details of all AEs and SAEs will be collected for a patient from the signing of the informed consent form (ICF) up to 90 days after the last dose of durvalumab. If an event starts after this period and the Investigator considers that it is possible that it is due to a late onset toxicity to durvalumab, then it should be reported as an AE or SAE.

All AEs will be coded using the latest version of Medical Dictionary for Regulatory Activities (MedDRA) providing the System Organ Class (SOC) and Preferred Term (PT).

In addition, all AEs will also be graded according to the National Cancer Institute (NCI) Common Terminology Criteria for AEs (CTCAE Version 4.03) allocating grades from Grade 1 to Grade 4 which will be used for the reporting. The meaning of these categories are as follows:

- Grade 1: Mild AE
- Grade 2: Moderate AE
- Grade 3: Severe AE
- Grade 4: Life-threatening or disabling AE
- Grade 5: Death related to AE

Treatment-emergent adverse events (TEAEs) are AEs that start after the first dose of durvalumab or which start prior to the first dose of durvalumab but worsen following the first dose of durvalumab, and where the start date/date of worsening is also no later than 90 days after the last dose of durvalumab or the initiation of the first subsequent therapy following discontinuation of durvalumab (whichever occurs first). Any TEAE will be included in the AE summaries as detailed in Section 4.5.1.

Missing start and stop dates for AEs will be imputed using the rules described in Section 4.1.3.

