### 3.2.8 Exposure to Durvalumab

The total (or intended) exposure (weeks) of durvalumab is defined as:

- Total treatment duration (weeks) = Total treatment duration (days) / 7

where:

Total treatment duration (days) = [earliest of (last dose date where dose > 0mg + 27 days, death date, cut-off date [DCO]) - first dose date] + 1

The actual exposure (weeks) of durvalumab is defined as:

- Actual treatment duration (weeks) = [total treatment duration (days) – total duration of dose delays (days)] / 7.

Dose reductions are not permitted per the CSP for durvalumab and the actual exposure calculation makes no adjustment for any dose reductions that may have occurred.

As patients are scheduled to receive 1500 mg via IV infusion every 4 weeks (28 days), the duration of dose delays is the sum of all individual dose delays as follows:

- Total duration of dose delays (days) = sum of MAX[0, (date of dose [x+1] – date of dose [x] - 28 days)].

If no delays were encountered, the total duration of dose delays would sum up to 0.

Relative dose intensity (RDI) is the percentage of the actual dose intensity delivered relative to the intended dose intensity through to treatment discontinuation.

RDI is defined as follows:

RDI = 100% \* d/D, where d and D are, respectively, the actual and intended cumulative doses delivered up to the date of durvalumab discontinuation or progressive disease or the data cut-off date, whichever occurs earlier. D is the total dose that would be delivered if there were no modification to dose or schedule.

Percentage intended dose (PID) is the percentage of the actual dose delivered relative to the intended dose through to disease progression.

PID = 100% \* d1/D1, where d1 is the actual cumulative dose delivered up to the earlier of progression (or a censoring event) or the data cut-off date and D1 is the intended cumulative dose up to the earlier of progression (or a censoring event) or the data cut-off date. D1 is the total dose that would be delivered, if there were no modifications to dose or schedule.

When deriving actual dose administered the volume before and after infusion will also be considered.

To illustrate the calculation of RDI, [Table 5](#) shows an example of durvalumab dosing for 4 patients.

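### The AE rate per 100 patient-years counts AEs and person-time over different periods, so its distortion depends on how long patients were treated

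*SAP*

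**What the plan says.** SAP 4.5.1 adds a rate to the all-AE table by preferred term (PT). The calculation is "The number of patients with an AE in each PT is divided by the sum of the actual exposure to durvalumab (days"), and then "This is multiplied by 365.25 x 100 to create an event rate per 100 patient years".

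**Numerator window.** The general rule at the head of SAP 4.5.1 includes "All AEs reported up until 90 days following completion or discontinuation of durvalumab treatment or until the initiation of the first subsequent therapy", whichever is first, unless an exception is stated. None is stated for the rate. The treatment-emergent definition in SAP 3.2.3 has the same limit: "no later than 90 days after the last dose of durvalumab or the initiation of the first subsequent therapy following discontinuation of durvalumab".

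**Denominator.** SAP 3.2.8 runs total treatment duration from first dose to the earliest of "last dose date where dose > 0mg + 27 days, death date, cut-off date". Actual exposure then removes delays: "Actual treatment duration (weeks) = [total treatment duration (days) – total duration of dose delays (days)] / 7", where the delay total is the "sum of MAX[0, (date of dose [x+1] – date of dose [x] - 28 days").

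SAP 4.1.1 summarises all safety data separately for the PS 0 to 1 and PS 2 groups, so the rate will appear in both columns.

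**The concern.** A rate has a plain meaning only if its two parts cover the same time. Here an AE starting on days 28 to 90 after the last dose, or during a dosing delay, can be counted although that time is missing from the denominator. The missing 63 days are a large share of a short exposure and a small share of a long one.

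This statistic is the one in the all-AE table that is meant to allow for unequal exposure between groups. If its distortion itself depends on exposure length, two columns with the same underlying AE rate can show different figures.

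There is a second problem. The numerator counts patients, once per PT, although the result is called an event rate, and the denominator keeps running after a patient's first onset. The result is neither an event rate nor a first-event incidence rate.

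**Working it through.** The documents give no AE rate, so there is no planned figure to reproduce. The check applies the SAP definitions directly.

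**Formulae.** Take k doses at 28-day intervals, with d days of delay in total. The last dose falls on day 1 + 28(k − 1) + d.

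- Actual exposure: E = [1 + 28(k − 1) + d] + 27 − d = 28k.
- AE window, with no subsequent therapy, death or data cut-off first: W = [1 + 28(k − 1) + d] + 90 = 28(k − 1) + d + 91.
- Difference: W − E = 63 + d.

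**Per patient.**

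| Doses | Delay (days) | W / E | Ratio |
|---|---|---|---|
| 1 | 0 | 91 / 28 | 3.25 |
| 4 | 0 | 175 / 112 | 1.56 |
| 10 | 0 | 343 / 280 | 1.23 |
| 26 | 0 | 791 / 728 | 1.09 |
| 7 | 0 | 259 / 196 | 1.32 |
| 7 | 28 | 287 / 196 | 1.46 |
| 26 | 28 | 819 / 728 | 1.13 |

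If one group all received 4 doses and another all received 10, with no delays and the same true rate throughout the window, the first would show a rate 1.5625 / 1.225 = 1.28 times the second.

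**Pooled over a cohort.** The SAP rate is a pooled figure, so the factor is ΣW / ΣE. Three dose distributions are assumed for 120 patients, 10 of them with the PT:

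- early stopping: 15, 30, 40, 25 and 10 patients with 1, 3, 7, 13 and 26 doses;
- mixed: 10, 15, 25, 30 and 40 patients with the same dose numbers;
- long: 10, 30 and 80 patients with 3, 13 and 26 doses.

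| Cohort | ΣE | ΣW | SAP rate | Matched rate | Factor | Factor with 28 days' delay* |
|---|---|---|---|---|---|---|
| Early | 27,160 | 34,720 | 13.5 | 10.5 | 1.28 | 1.39 |
| Mixed | 46,480 | 54,040 | 7.9 | 6.8 | 1.16 | 1.23 |
| Long | 70,000 | 77,560 | 5.2 | 4.7 | 1.11 | 1.16 |

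*In every patient with 2 or more doses. Rates are per 100 patient-years, for example 10 / 27,160 × 36,525 = 13.5.

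**Effects in the other direction.**

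- *Subsequent therapy.* It ends AE counting but not exposure. If it starts 14 days after the last dose with no delay, W / E is 15/28 = 0.54 (1 dose), 71/84 = 0.85 (3 doses) and 183/196 = 0.93 (7 doses).
- *Person-time after first onset.* The SAP rate was divided by a first-event rate, assuming a constant hazard over W and no delays. The 18.3% and 33.9% are the diarrhoea and pneumonitis or radiation pneumonitis incidences that Protocol 2.3.2.1 gives for durvalumab in the PACIFIC study; 5% is an assumption.

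| Cohort | PT incidence 5% | 18.3% | 33.9% |
|---|---|---|---|
| Early | 1.23 | 1.11 | 0.96 |
| Mixed | 1.12 | 1.02 | 0.88 |
| Long | 1.08 | 0.99 | 0.89 |

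**Delay rule.** A delay later made up by shorter intervals, which Protocol 1.2 allows down to 22 days, is still subtracted. Doses on days 1, 39, 61 and 85 have intervals of 38, 22 and 24 days, so 10 days are removed. Exposure is 85 + 27 − 10 = 102 days, against 112 calendar days.

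**The case against.** The strongest reply is that the direction is not uniform. A reader might infer that every rate is inflated, and most of all in early stoppers. The documents do not support that:

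- A patient who moves to new therapy within 27 days of the last dose has the opposite error, and it is proportionally largest after few doses.
- A patient still on treatment at data cut-off, or who dies within 27 days of the last dose, has no mismatch apart from delays.
- A PT with no first onset in the uncounted time has no surplus in its numerator.
- For common PTs, the retained person-time can outweigh the missing time.

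All of this stands. The cut-off exemption matters less at the final analysis, which SAP section 5 places after the last patient's possible 24 months and a 90-day follow-up; by then most windows will have closed.

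A reader might also infer that delays and early stops reflect toxicity, and that PS 2 will be the column most affected. Neither is established. The plan allows delays for reasons other than treatment-related AEs (Protocol 1.2, SAP 1.2.1) and stopping for progression, withdrawal of consent or alternative therapy (Protocol 1.1 and 7.1). It gives no expected treatment duration by PS group.

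The consequence is also limited. This is one descriptive statistic in a table that also gives n (%). No hypothesis is tested (Protocol 9.1), and the primary endpoint is a proportion with a Clopper-Pearson interval (SAP 4.3).

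These points narrow the concern but do not remove it. Opposing errors whose balance shifts with PT frequency, treatment duration and time to next therapy cannot be corrected by a reader of the table.

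**Conclusion.** The mismatch holds as a matter of definition. Up to 63 days (90 − 27) per patient who stops, plus all delay days, can contribute AEs but no person-time. Without delay, subsequent therapy, death or cut-off in the window, the ratio falls from 3.25 at 1 dose to 1.09 at 26 doses. In the assumed cohorts, the pooled effect against a window-matched denominator is a factor of 1.11 to 1.39. Those cohort figures rest on assumed dose distributions and delays; the first-event comparison also assumes a constant hazard.

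The conclusion is that the distortion varies with treatment duration and can differ between the PS columns. It is not that all rates are too high. The net effect for a given PT may be in either direction. The statistic is secondary and descriptive, but it is wrong as written and should be corrected before the tables are produced.

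**What to change.** Use one window for both parts of the rate, with delay days included. Either option works:

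1. **On-treatment rate.** Count only AEs with onset from first dose to the earliest of last dose + 27 days, death or data cut-off, over the calendar days in that period. If AEs after subsequent therapy stay excluded, person-time must stop there too.
2. **Current AE window.** Keep the AE rule and use days from first dose to the earliest of last dose + 90 days, first subsequent therapy, death or data cut-off.

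In both, because patients rather than events are counted, stop a patient's person-time at first onset of the PT and label the result *patients with event per 100 patient-years at risk*. Define the quantity in days: SAP 4.5.1 asks for days, while SAP 3.2.8 expresses actual exposure in weeks.

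The cost is SAP wording and a derived time at risk, needed for each patient and PT if person-time stops at first onset. No new data are required. Rates may fall or rise, depending on the PT.
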